## 7. RATIONALE AND BACKGROUND

The development of vaccines against SARS-CoV-2 has been critical to ending the Coronavirus disease 2019 (COVID-19) pandemic. In the United States (US), the first to become available were the messenger RNA (mRNA) vaccines BNT162B2 (COMIRNATY) (Pfizer Inc/BioNTech, 2023) and mRNA-1273 (Moderna US, Inc., 2023). Authorized for emergency use by the US Food and Drug Administration (FDA) on 11 December 2020 and 18 December 2020, respectively, these first-generation vaccines contained a piece of the original SARS-CoV-2 virus's mRNA, instructing cells in the body to make the virus's distinctive "spike" protein and triggering an immune response (FDA, 2020a, 2020b; Nabizadeh et al., 2023). Beginning in August 2022, in response to the new circulating Omicron variant of SARS-CoV-2, the vaccines were adapted to add an mRNA component from the Omicron lineages BA.4 and BA.5, in addition to mRNA from the original viral strain, and were thereafter referred to as bivalent vaccines (FDA, 2022b, 2022c, 2022d). In September 2023, the COMIRNATY 2023-2024 Formula was approved for individuals  $\geq 12$  years of age. The Pfizer-BioNTech COVID-19 Vaccine 2023-2024 Formula was authorized under emergency use in individuals 6 months through 11 years of age. This new formulation contains a monovalent (single) mRNA component corresponding to the Omicron variant XBB.1.5 (FDA, 2023b). The Omicron XBB sublineage accounted for nearly all COVID-19 cases in the US in spring 2023 and remained the most common variant as of 08 July 2023 (CDC, 2020).

Based on data from the original COMIRNATY formula, the US prescribing information for COMIRNATY highlights the following warnings and precautions:

- "Postmarketing data demonstrate increased risks of myocarditis and pericarditis"
- "Syncope (fainting) may occur in association with administration of injectable vaccines, including COMIRNATY." (Pfizer Inc/BioNTech, 2023)

Additionally, the following serious adverse events have been observed after immunization with the Pfizer-BioNTech, Moderna, and Janssen vaccines as reported in the Vaccine Adverse Event Reporting System (VAERS): glomerulonephritis, herpes zoster, immune-mediated myositis, and relapsing or progressing MS (VAERS, 2023). More information is needed on whether the safety profile of the COMIRNATY 2023-2024 Formula remains consistent with the safety profile of the original formula in the overall population and subpopulations of interest.

Pfizer/BioNTech, sponsor of the first COVID-19 vaccine to be authorized in the US, is conducting a non-interventional PASS to collect information on the safety profile of its most recently authorized strain of the COVID-19 vaccine, the Omicron XBB.1.5 monovalent vaccine (COMIRNATY 2023-2024 Formula; Pfizer Inc/BioNTech, 2023). This combined protocol and statistical analysis plan (SAP) describes a non-interventional observational study using claims data from a large US insurer to evaluate the safety of the COMIRNATY 2023-2024 Formula in the general population as well as in subpopulations of interest. This

non-interventional study is designated as a PASS and is a condition of authorization to the FDA.

## **8. RESEARCH QUESTION AND OBJECTIVES**

The research question of this study is: What is the incidence of pre-specified safety events of interest among individuals who receive the COMIRNATY 2023-2024 Formula in the United States? To answer this question, the study will be conducted in two phases, each with its own specific objectives.

### **8.1. Phase 1**

Phase 1 will be designed to sequentially monitor the occurrence of pre-specified safety events of interest following vaccination.

#### **8.1.1. Primary Objective:**

- To estimate the incidence of pre-specified safety events of interest following vaccination with the COMIRNATY 2023-2024 Formula compared to the incidence of these events during a control window (i.e., expected rates of these events).

### **8.2. Phase 2**

Phase 2 will be designed to assess the risk of pre-specified safety events of interest among individuals who receive the COMIRNATY 2023-2024 Formula compared to individuals with no recorded vaccination for the COMIRNATY 2023-2024 Formula for up to 1 year after vaccination.

#### **8.2.1. Primary Objective:**

- To estimate the incidence of pre-specified safety events of interest among individuals who receive the COMIRNATY 2023-2024 Formula compared to individuals with no recorded vaccination for the COMIRNATY 2023-2024 Formula.

#### **8.2.2. Secondary Objective:**

- To estimate the incidence of pre-specified safety events of interest among individuals who receive the COMIRNATY 2023-2024 Formula compared to individuals with no recorded vaccination with the COMIRNATY 2023-2024 Formula among subgroups of individuals with concomitant administration of a non-COVID-19 vaccine; immunocompromised individuals; individuals with specific comorbidities; individuals with prior SARS-CoV-2 infection; individuals with prior COVID-19 vaccination; pregnant women; pediatric subjects; and the elderly, if sample size permits.

## 9. RESEARCH METHODS

### 9.1. Study Design

This non-interventional study will be conducted in two phases. Phase 1 will include a study of self-controlled risk interval (SCRI) design conducted using a pre-adjudicated claims database for the interim report. For the final report, the SCRI study will be repeated using the ORD, an adjudicated claims database. Phase 2 will be a comparative safety cohort design using the ORD and will also be included in the final report.

Table 1 summarizes the study designs and data sources included in the interim and final reports. These two different study designs are complimentary, each with its own strengths. The SCRI design is less impacted by misclassification of COVID-19 vaccine exposure and confounding by time-fixed characteristics, while the cohort study design enables a longer follow-up period.

**Table 1. Study design and data sources for interim and final reporting**

[figure not shown]
	Interim Report	Final Report
Study Design	SCRI (Section 9.1.1)	SCRI (Section 9.1.1) Cohort ( Section 9.1.2 )
Data Source	Optum pre-adjudicated claims database ( Section 9.4.1 )	ORD (adjudicated) database ( Section 9.4.2 )

#### 9.1.1. SCRI

Phase 1 will monitor the incidence rate of pre-specified safety events of interest in a general population of individuals who receive the COMIRNATY 2023-2024 Formula using an SCRI study design that tracks post-vaccination risk intervals and control (reference) periods for each vaccinated individual. Monitoring will be conducted during a pre-specified risk period immediately following vaccination, and the observed rate of events during this risk period will be compared to that of a control period temporally removed from the vaccination event. As depicted in [Figure 1](#), only individuals who receive the COMIRNATY 2023-2024 Formula will be included in the SCRI study ([Baker et al., 2015](#)). Within each individual, outcomes occurring during the risk interval will be compared with those occurring during the control period, in order to determine whether these outcomes occur more frequently immediately after vaccination as compared with a reference period. A washout period may be inserted between the risk interval and the control period to ensure that events relating to the vaccine are not incorrectly attributed to the control period. To ensure that observed outcomes are truly incident, a period free from the outcome of interest (clean period) may be required prior to vaccination.

090177e1a5be86fe\Approved\Approved On: 19-Mar-2026 15:57 (GMT)

**Figure 1. Self-controlled risk interval design**

Certain individuals (i.e., immunocompromised patients aged 6 months through 11 years; [FDA, 2023b](#)) may receive more than one dose of the COMIRNATY 2023-2024 Formula and thus may have multiple risk and control periods. For these individuals, analysis may be conducted using the first dose and repeated by pooling the multiple risk periods, as well as the control periods.

The safety outcomes of interest, along with relevant clean windows, risk intervals, and washout and control periods, are listed in [Section 9.3.2](#).

### 9.1.2. Cohort Design

Phase 2 will consist of a propensity score-matched cohort study of individuals with and without a recorded dose of the COMIRNATY 2023-2024 Formula, conducted within the ORD. During the accrual period of 11 September 2023 through 31 March 2024, individuals who receive the COMIRNATY vaccine will be classified as exposed, and those with no recorded vaccination with the COMIRNATY 2023-2024 Formula but who have a healthcare encounter will be classified as comparators. Propensity score matching will be performed to address control of potential confounding, with matching to be conducted within age group and calendar periods. Age group will be defined as: 6 months–4 years; 5–11 years; 12–17 years; 18–64 years; and  $\geq 65$  years, while calendar periods will be defined by 14-day increments (e.g., 01 September 2023 to 14 September 2023, 15 September 2023 to 28 September 2023). Alternate calendar periods (e.g., one month) may be empirically explored. Thus, within any given calendar period, comparators within the same age group will be matched without replacement to a COMIRNATY recipient on PS, down to a maximum allowable level of precision in the PS ([Section 9.7.2.1](#)). This will ensure a sufficient pool of comparators for stratified and/or subpopulation analyses ([Sections 9.7.2.3 & 9.7.2.4](#)).

These matched cohorts will be followed for up to one year for occurrence of safety outcomes. For this Phase 2 matched cohort study, the safety outcomes of interest are listed in [Section 9.3.2](#).

090177e1a5be86fe\Approved\Approved On: 19-Mar-2026 15:57 (GMT)

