#### **9.2.5. Follow-Up Period**

##### **9.2.5.1. SCRI**

In the SCRI analysis, follow-up for the risk period will begin upon (for the outcomes of anaphylaxis and convulsions/seizures) or one day after (for all other outcomes) receipt of the COMIRNATY 2023-2024 Formula ([Table 2](#)) and continue until the earliest of:

- Receipt of a COVID-19 vaccine other than the COMIRNATY 2023-2024 Formula;
- The end of the outcome-specific risk interval as defined in [Section 9.3.2](#);
- Disenrollment from the health plan, death, or the end of data collection.

After the outcome-specific pre-specified washout period following the risk interval, follow-up for the control period will begin and continue until the earliest of:

- Receipt of a COVID-19 vaccine other than the COMIRNATY 2023-2024 Formula;
- The end of the control period as defined in [Section 9.3.2](#);
- Disenrollment from the health plan, death, or the end of data collection.

Individuals will be followed for each safety outcome during both the risk and control periods, such that events observed during the risk period or washout period will not censor follow-up for the control period.

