### 9.2.5.2. Cohort Study

In the cohort study (Phase 2), depending on the safety outcome of interest, follow-up will begin on cohort entry or the day following cohort entry ([Table 2](#)) and extend until the earliest of:

- The occurrence of an outcome of interest ([Section 9.3.2](#));
- For COMIRNATY 2023-2024 Formula recipients, receipt of a COVID-19 vaccine other than the COMIRNATY 2023-2024 Formula; for comparators whose qualifying healthcare encounter is for a non-COMIRNATY 2023-2024 Formula COVID-19 vaccination, receipt of a different brand of COVID-19 vaccine from cohort entry;
- One year after cohort entry;
- Disenrollment from the health plan, death, or the end of data collection;

Those comparators who later receive a dose of COMIRNATY 2023-2024 Formula may be eligible for inclusion in the COMIRNATY 2023-2024 Formula cohort if they meet the eligibility criteria for cohort entry.

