### 9.3.2. Outcomes

In both the SCRI and cohort studies, the pre-specified safety outcomes of interest will include the following:

- ADEM
- Anaphylaxis
- Bell's palsy
- CVST
- Convulsions/seizures (non-febrile)
- Encephalomyelitis
- Glomerulonephritis
- Guillain-Barré syndrome
- Herpes zoster
- Immune-mediated myositis
- Immune thrombocytopenia
- Kawasaki disease
- Multi inflammatory syndrome (in children and adults)
- MS
- MI
- Myocarditis/pericarditis
- PE
- Stroke, hemorrhagic
- Stroke, ischemic
- Transverse myelitis

In addition, in Phase 2 of the study, the following pregnancy outcomes will be assessed in pregnant women or their infants, if sample size permits:

- Spontaneous abortion
- Stillbirth
- Preterm birth
- Major congenital malformations
- Small for gestational age

Code lists for the safety outcomes of interest are provided in [Annex 2 \(Appendix III\)](#). Corresponding site of care requirements are listed in Table 2. When possible, outcomes will be defined using a validated claims-based algorithm with high performance ([CBER, 2021](#)).

If a safety signal is detected in the interim report, then medical records will be retrieved for a subset of participants to confirm the presence of that study outcome. A safety signal that requires confirmation through medical record review will be defined as a rate ratio of > 3.0 and a corresponding P value of < 0.01 in the primary analysis of the SCRI design (details in [Section 9.7.1.1](#)). Additionally, medical record review may be conducted for analyses beyond the primary SCRI analysis if a safety signal (defined as a rate ratio of > 3.0 and a corresponding P value of < 0.01) is detected in the interim or final report. Medical records may also be retrieved for AESIs with estimates approaching the pre-specified safety signal threshold.

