**Table 2. Clean periods and risk intervals for safety outcomes of interest**

Outcome	Clean Period*	Vaccine Risk Interval*	Care Setting**
Pulmonary embolism	Days -365 to 0	Days 1 to 28	IP, OP
Stroke, hemorrhagic	Days -365 to 0	Days 1 to 28	IP
Stroke, ischemic	Days -365 to 0	Days 1 to 28	IP
Transverse myelitis	Days -365 to 0	Days 1 to 42	IP, ED

\*Expressed in relation to the day of vaccination or cohort entry (Day 0). When more than one vaccine risk interval had been cited in the prior literature, the present risk interval was chosen from the prior literature using the following order of priority for all outcomes other than myocarditis/pericarditis: 1) CBER 2021; 2) the most frequently cited risk interval in prior literature; and 3) the shortest risk interval cited in prior literature. The risk interval for myocarditis/pericarditis was chosen based on [CBER 2022](#).

\*\*IP, Inpatient; ED, Emergency department visit; OP, Outpatient facility claims and professional/provider claims.

\*\*\*Could not be determined from the literature, so modeled after other outcome intervals in [CBER 2021](#).

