#### **9.7.2.2. Primary Analysis**

Once the matched cohorts have been created, the incidence rate of each safety outcome will be estimated among the COMIRNATY 2023-2024 Formula-exposed group and its matched comparator group. The rate ratio will be estimated using unconditional Poisson regression that accounts for both the matching ratio (i.e., a weight representing the number of COMIRNATY 2023-2024 recipients divided by the number of comparators in each individual strata) and individuals who are included in both study cohorts (i.e., using a REPEATED statement with an independent working correlation structure). If standardized differences show covariate imbalances in the matched cohorts, imbalanced covariates will be included in the unconditional Poisson models.

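### Phase 2 gives acute outcomes only a one-year rate ratio, which dilutes short-interval risks, and the subgroup and alternative-comparator analyses have nothing else to rest on

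*Protocol*

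**What the plan says.** **Outcomes.** Section 9.3.2 gives the two designs one list of 20: "In both the SCRI and cohort studies, the pre-specified safety outcomes of interest will include the following".

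**Risk intervals.** Table 2 sets them at 2 days (anaphylaxis), 21 days (e.g. myocarditis/pericarditis), 22, 28 or 30 days, and 42 days (e.g. Guillain-Barré syndrome). The footnote says they are "Expressed in relation to the day of vaccination or cohort entry (Day 0", so they are defined for the cohort as well as for the SCRI.

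**End of follow-up.** Section 9.1.2 says of the Phase 2 cohort: "These matched cohorts will be followed for up to one year for occurrence of safety outcomes". For the SCRI, Section 9.2.5.1 lists "The end of the outcome-specific risk interval as defined in" Section 9.3.2 as a stopping point. Section 9.2.5.2 has no such item for the cohort. Its fixed time limit is "One year after cohort entry", and it cites Table 2 only for the day on which follow-up starts.

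**Analysis.** Section 9.7.2.2 says "the incidence rate of each safety outcome will be estimated among the COMIRNATY 2023-2024 Formula-exposed group and its matched comparator group", followed by one Poisson rate ratio. Neither it nor Sections 9.7.2.3 and 9.7.2.4 restricts the time at risk.

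**Record-review trigger.** Section 9.3.2 requires record review for a signal in the interim report, "defined as a rate ratio of > 3.0 and a corresponding P value of < 0.01 in the primary analysis of the SCRI design". It also allows review in other analyses on a "safety signal (defined as a rate ratio of > 3.0 and a corresponding P value of < 0.01"), and for estimates that come near that threshold.

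**The concern.** When an excess occurs only in the first days or weeks, a ratio over a year averages it with ten to twelve months of background rate. The estimate then describes average one-year incidence and says little about the acute period.

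For the whole vaccinated population this loss is covered, because the SCRI examines each outcome in its own interval. Elsewhere it is not. Section 9.7.1 specifies only a primary SCRI analysis. The subgroups (under 18, 65 and over, pregnant, immunocompromised and others) are analysed only in Section 9.7.2.4. The comparisons with other COVID-19 vaccines, non-COVID-19 vaccines and outpatient visits appear only in Section 9.7.2.3. The protocol's sole secondary objective (Section 8.2.2) therefore rests on one-year ratios. Myocarditis in under-18s is the clearest case: the label carries a warning (Section 7), the interval is 21 days, and that subgroup has no other planned estimate.

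**Working it through.** The protocol states no expected rate ratio, event count or power, so there is no planned figure to reproduce.

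**Inputs from the protocol.** Risk interval w = 2, 21, 28 or 42 days (Table 2); follow-up F = 365 days (Section 9.2.5.2); trigger RR > 3.0 with P < 0.01 (Section 9.3.2).

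**Assumptions.** Rare events, a constant background rate λ, no excess after the interval, and full follow-up. The in-interval ratio RRw is varied.

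**Step 1: dilution.** Expected events per exposed person are λ(RRw·w + F − w), against λF per comparator. Hence

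RR over follow-up = 1 + (RRw − 1)·w/F.

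For example, RRw = 3 and w = 21 give 1 + 2 × 21/365 = 1.115.

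| Interval | RRw = 3 | RRw = 5 | RRw = 10 |
|---|---|---|---|
| 2 days | 1.01 | 1.02 | 1.05 |
| 21 days | 1.12 | 1.23 | 1.52 |
| 28 days | 1.15 | 1.31 | 1.69 |
| 42 days | 1.23 | 1.46 | 2.04 |

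**Step 2: what the 3.0 trigger needs.** Setting the ratio to 3 gives RRw = 1 + 2F/w.

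| Interval | F = 365 | F = 180 |
|---|---|---|
| 2 days | 366 | 181 |
| 21 days | 35.8 | 18.1 |
| 28 days | 27.1 | 13.9 |
| 42 days | 18.4 | 9.6 |

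The second column shows the effect if mean follow-up were only 180 days.

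**Step 3: what is lost.** Assume 1:1 matching, 50 comparator events per year, Poisson counts and an exact two-sided P value. The comparator count expected inside the interval is 50·w/365, i.e. 5.8 for 42 days and 2.9 for 21 days.

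| Case | Criterion | One year | Interval only |
|---|---|---|---|
| 42 days, RRw = 10 | RR > 3.0 and P < 0.01 | 0.017 | 0.9998 |
| 21 days, RRw = 10 | RR > 3.0 and P < 0.01 | 0.0003 | 0.99 |
| 42 days, RRw = 5 | P < 0.01 alone | 0.28 | 0.92 |
| 21 days, RRw = 10 | P < 0.01 alone | 0.36 | 0.99 |

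The last two rows show that the loss does not come only from the 3.0 threshold. Under these assumptions, the later follow-up adds background events faster than it adds information. Anaphylaxis is the exception to the gain: with RRw = 10, only 50 × 2/365 = 0.27 comparator events are expected in the interval, and the trigger fires with probability 0.0055 even there.

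**The case against.** **The year is deliberate.** Section 8.2 frames Phase 2 as risk for up to one year. Section 9.1 calls the designs complementary, with longer follow-up as the cohort's strength. Section 9.9 makes the cohort primary for chronic outcomes. A reader might infer that Phase 2 fails its own objective; it does not, because one-year incidence is that objective. This stands. However, no section says outright that the SCRI is primary for acute outcomes, while Section 9.7.2.2 makes the one-year ratio the primary Phase 2 result for all 20.

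**The SCRI already covers acute risk.** It uses each outcome's own interval and is repeated in the Optum Research Database for the final report. This stands for the overall population, so it would be wrong to infer that acute signals are lost from the study. It does not reach the subgroups or alternative comparators.

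**The trigger can fire and is optional.** Step 2 shows that it fires above an in-interval RR of about 18 for 42-day outcomes, and lower with shorter follow-up. In Phase 2 it only permits record review, estimates near it may also be reviewed, and all ratios are reported regardless. The plan would therefore not be blind to large acute risks. Nor does anything here show that the threshold itself should be replaced; that question is separate from follow-up length.

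**A diluted ratio is still detectable with enough events.** With 1:1 matching, two-sided 5% and 80% power, the comparator events needed are about 7.85 × (1 + 1/R)/(ln R)². That gives roughly 720 for R = 1.153 and 330 for R = 1.230. The point is fair for common outcomes. Inside the interval, however, R = 3 needs only 7.85 × 1.333/1.207 ≈ 8.7 events (a rough figure at such counts). That corresponds to 8.7 × 365/28 ≈ 113 comparator events per year for a 28-day outcome and 8.7 × 365/42 ≈ 76 for a 42-day one.

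**Late excess is possible, and some intervals are uncertain.** Both are true. They argue for keeping the one-year ratio, not for omitting the interval-restricted one. Table 2 says that the risk intervals for glomerulonephritis and multiple sclerosis (MS) could not be determined from the literature, so those two should not be truncated.

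**Conclusion.** The point holds as a gap in Phase 2. It does not show that the study cannot detect acute harm. If the excess is confined to the Table 2 interval and the background rate is constant, in-interval ratios of 3 to 5 read 1.01 to 1.46 over a full year. The RR > 3.0 trigger is then practically insensitive for in-interval ratios below about 18 to 36 at intervals of 42 to 21 days. "Near 1" would be too strong in general, since an RR of 10 over 42 days still reads 2.04. Excess after the interval would raise the one-year ratio, and shorter follow-up would reduce the dilution. The firing probabilities rest on an assumed 50 comparator events per year. The consequence falls on the subgroup and alternative-comparator analyses, which have no undiluted estimate of acute risk.

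**What to change.** - **Sections 9.2.5.2 and 9.7.2.2 to 9.7.2.4:** for acute outcomes, add a rate ratio with follow-up ending at the Table 2 risk interval. Report it beside the one-year ratio and carry it through the secondary and subgroup analyses.
- **Chronic outcomes:** keep one year as primary for chronic outcomes such as MS. Treat as chronic any outcome whose risk interval Table 2 marks as not determinable from the literature, such as glomerulonephritis. List which outcomes fall in each class, since Section 9.9 gives only an example.
- **Roles of the designs:** state that the SCRI is primary for acute outcomes.
- **Section 9.3.2:** for acute outcomes in Phase 2, apply the RR > 3.0 trigger to the interval-restricted ratio, not the one-year ratio.

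**Cost.** Protocol wording and one further follow-up cut-off per acute outcome, on data already extracted. The interval-restricted estimates will have fewer events and wider confidence intervals, most of all in small subgroups, and anaphylaxis gains little.
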